#### 13.6.2.2 Non fatal and non life-threatening SUSARs

All other SUSARs and safety issues must be reported to the competent authority and Ethics Committee in the concerned member state as soon as possible but no later than **15 calendar days** after first knowledge of the minimum criteria for expedited reporting. Further relevant follow-up information should be given as soon as possible.

### 13.6.3 How to report?

#### 13.6.3.1 Minimum criteria for initial expedited reporting of SUSARs

Information on the final description and evaluation of an adverse reaction report may not be available within the required time frames for reporting. For regulatory purposes, initial expedited reports should be submitted within the time limits as soon as the minimum following criteria are met:

- a) A suspected investigational medicinal product,
- b) An identifiable subject (e.g. trial subject code number),
- c) An adverse event assessed as serious and unexpected, and for which there is a reasonable suspected causal relationship,
- d) An identifiable reporting source, and, when available and applicable:

- A unique clinical trial identification (EudraCT number or in case of non-European Community trials the sponsor's trial protocol code number)

- A unique case identification (i.e. sponsor's case identification number).

#### 13.6.3.2 Follow-up reports of SUSARs

In case of incomplete information at the time of initial reporting, all the appropriate information for an adequate analysis of causality should be actively sought from the reporter or other available sources. Further available relevant information should be reported as follow-up reports. In certain cases, it may be appropriate to conduct follow-up of the long-term outcome of a particular reaction.

#### 13.6.3.3 Format of the SUSARs reports

Electronic reporting, when available, is the expected method for expedited reporting of SUSARs to the CA. The format and content as defined by the CA should be adhered to.

### **13.7 Pregnancy Reporting**

All pregnancies within the trial (either the trial participant or the participant's partner) should be reported to the Chief Investigator and the Sponsor using the relevant Pregnancy Reporting Form within 24 hours of notification.

Pregnancy is not considered an AE unless a negative or consequential outcome is recorded for the mother or child/foetus. If the outcome meets serious criteria, this would be considered an SAE.

### **14 Toxicity – Emergency Procedures**

In the event of toxicity reactions, standard medical practices will be employed, including emergency care and hospitalization if needed. All medications in this study are licensed for use in medicine and their uses are familiar to the physicians and staff at all participating centres.

### **15 Evaluation of Results**

The primary endpoint is the time to relapse (including both major and minor – see definitions in section 15.1) from randomisation. This will be reported when all subjects have completed the 24 month treatment phase of the study.

#### **15.1 Response Criteria**

##### 15.1.1 Remission

For the purpose of this study, and progression to randomisation for allocation to one of the two arms of the maintenance phase of the study, remission equates to achievement of disease control (defined as a BVAS/WG  $\leq$  1 and daily prednisone dose  $\leq$  10mg) by month 4.

##### 15.1.2 Major relapse

Major relapse is defined as the development of a new or recurrent major disease activity item using the BVAS/WG that in the opinion of the investigator requires treatment with > prednisone 20mg/day for any period of time and/or increase in dose of immunosuppressive medication and/or addition or substitution of another immunosuppressive medication.

Subjects experiencing a major relapse will have met the end point of the trial. Further treatment decisions are made by the investigator and are not determined by the protocol. All patients will continue to be followed for safety purposes.

### 15.1.3 Minor relapse

Minor Relapse = "Any increase in disease activity that does not meet the definition of Major Relapse."

Although subjects experiencing a minor relapse will have met the trial end-point they will remain in the trial on the following protocol (Relapse Schedule): minor relapses will be treated with an increase in prednisone to 20 mg/day for 7 days, reducing by 2.5 mg every week back to 5 mg/day . Treatment of a minor relapse will be allowed only *once* during the trial period. At the time of a second minor relapse, further treatment decisions are made by local investigators and are not determined by the protocol. All patients will continue to be followed for safety purposes.

## 16 Statistics

### 16.1 Statistical Methods

The study will have a 24 month recruitment period. The minimum follow-up period will be 24 months of treatment plus 12 months post-treatment, totalling 36 months. The maximum follow-up period will be 24 months of treatment plus 24 months post-treatment, totalling 48 months.

The primary intention to treat analysis will be based on a Cox proportional hazard model. There will be a closed testing procedure, first the null hypothesis will be for a hazard ratio of 1 at all time points. If this is rejected at a 5% level then two further sub-hypotheses will be examined using time-varying covariates:

1. A hazard ratio of 1 up to 24 months post-randomisation (i.e. during treatment).
2. A hazard ratio of 1 after 24 months post-randomisation (i.e. post-treatment).

A detailed statistical analysis plan will be produced before the final data base lock and this plan will include sub-group analyses and handling of missing or spurious data.

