## 8 Rationale for Trial

Rituximab is an established induction agent in AAV, especially for those with relapsing disease. Its role as a maintenance agent is less clear. 50% will pursue a chronic relapsing course with 77% relapsing a second time within 2 years of a single course of rituximab. *Therefore the major unmet need is prevention of future relapse in relapsing patients.* Pilot data suggests that 6 monthly rituximab over 2 years is effective, safe, and leads to sustained treatment free remission. This is the platform for definitive study in a controlled trial which, if positive, will re-define remission therapy for AAV. Relapses however did still occur, the vast majority (90%) within the 2 months preceding subsequent rituximab doses, and so a 4 monthly repeat dosing strategy has been adopted for the study.

The study aims to improve outcomes for AAV patients by comparing a rituximab regimen to the current standard of care – azathioprine or methotrexate and glucocorticoids. In addition to answering the primary question of which is the superior therapy for preventing relapse in AAV, a number of key secondary questions will be addressed:

- Does sustained rituximab therapy have long-term benefit beyond the treatment period?
- Is sustained rituximab safe?
- What is the optimal remission therapy after rituximab induction?

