### 9.6 Trial Endpoints

#### 9.6.1 Primary endpoint

The primary endpoint is the time to disease relapse (either minor or major relapse) from randomisation. Any patients who have not relapsed at study close will be censored. Further details of how relapse/censoring dates will be defined are given below.

A blinded Independent Adjudication Committee will be convened to look at all endpoint data.

Situation	Date of Relapse or Censoring	Outcome
No baseline assessments	Randomization	Censored
Relapse documented between scheduled visits	Unscheduled visit date	Relapsed
Drop-out with no relapse	Date of last assessment with no documented relapse	Censored
Treatment discontinuation for undocumented relapse	Date of last assessment with no documented relapse	Censored
Treatment discontinuation for toxicity or other reason, or protocol deviation	The patient will be followed up as per protocol and date of relapse or censoring observed accordingly	Relapsed/censored
Death due to relapse	Date of Death	Relapsed
Death due to other causes	Date of Death	Censored
Death or progression after More than one missed visit	Date of last assessment with no documented relapse	Censored

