### 16.3 Number of Subjects to be Enrolled

Enrolment will be ongoing until at least 160 patients are randomised. It is anticipated 190 patients will be required to be recruited to meet the goal of 160 patients randomized. Any patients in the induction phase when enrolment is halted will continue to follow the protocol and be randomised if the relevant criteria are met.

A power of 90% is achieved under the alternative hypothesis of a hazard ratio of 0.42 at the 5% significance level with 58 observed relapses. Randomising 160 patients will achieve this over the course of the study assuming a drop-out rate up to 5% at 2 years and a relapse-free rate of 75% and 50% at 4 years in the experimental and control arms respectively.

Based on data from the Cambridge cohort study, the overall hazard ratio is estimated (95% confidence interval) as 0.230 (0.116, 0.458) based on 37 observed relapses. For the early period the hazard ratio estimate is 0.210 (0.098, 0.449) based on 30 observed relapses. For the late period the hazard ratio estimate is 0.323 (0.061, 1.729)

based on seven observed relapses. Hence the sample size/power calculations are robust as they are based on a hazard ratio of 0.42 under the alternative hypothesis; the value of 0.42 is at the upper end of the confidence intervals for the overall and early period hazard ratios from the pilot data. The projected drop-out rate is based on the recently published EUVAS IMPROVE trial (16). It justifies the assumption of a rate below 5% in the second year.

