### 10.1 Primary efficacy analysis

The primary efficacy outcome measure of the trial is relapse-free survival, where a relapse is either major or minor (see definitions above). **The primary analysis will be a Cox regression model adjusted for the stratification factors (ANCA type, relapse severity and prednisone induction regimen) for the difference in the distribution of relapse-free survival between the rituximab arm and the azathioprine (control) arm (two-sided at  $\alpha$ -level of 5%).** Assuming a proportional hazard holds, the hazard ratio together with the 95% confidence interval will be estimated using a Cox regression model adjusted for the stratification factors.

There will be a closed testing procedure, first the null hypothesis will be tested for a hazard ratio of 1 at all time points. If this is rejected at a 5% level then two further sub-hypothesis will be examined using time-varying covariates:

1. A hazard ratio of 1 up to 20 months post-randomisation (i.e. during treatment).
2. A hazard ratio of 1 after 20 months post-randomisation (i.e. post-treatment).

Kaplan-Meier estimates for relapse-free survival at 24 and 48 months and median relapse-free survival with the corresponding 95% confidence intervals by treatment allocation will be presented.

Additional analyses will consider in turn the interaction of treatment with each of the three stratification variables, i.e. ANCA type, relapse severity and induction regimen. Frequency tables and Kaplan-Meier plots, as well hazard ratios and 95%

---

 Time measured from enrolment, in reality this corresponds to 20 months and 44 months post-randomisation.

confidence intervals of a Cox proportional hazard model including interactions will be presented. These results are to be taken as exploratory only, as these analyses were not planned in the protocol, are likely under-powered and are not adjusted for multiple comparisons.

The following tables and figures will be reported, taking into account events occurring after randomisation (i.e. excluding the induction phase):

- No. of relapses:
  - a) by type (major or minor)
  - b) by phase (during treatment or post-treatment)
  - c) per participant
- No. of participants with a relapse (major or minor) by type at:
  - a) All time points
  - b) During treatment (up to month 20 post-randomisation)
  - c) Post-treatment (after 20 months post-randomisation)

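### The gated post-treatment hazard ratio conditions on being relapse-free at the cut, so it needs a label and a randomised between-arm contrast beside it

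*Protocol*

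**What the plan says.** Protocol 9.6.1 defines the endpoint: "The primary endpoint is the time to disease relapse (either minor or major relapse) from randomisation". Protocol 16.1 fits a Cox model and tests a hazard ratio of 1 at all times. It then adds: "If this is rejected at a 5% level then two further sub-hypotheses will be examined using time-varying covariates". The second sub-hypothesis is "A hazard ratio of 1 after 24 months post-randomisation (i.e. post-treatment"). SAP 8.9 repeats the 24-month cut, but SAP 10.1 has "A hazard ratio of 1 after 20 months post-randomisation (i.e. post-treatment"), and SAP 5.2.1 fixes treatment duration at 20 months after randomisation. Under SAP 8.4 the models adjust for ANCA type, relapse severity and prednisone regimen only.

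Durability is a stated aim. Secondary objective 1 concerns sustained remission after the 24-month treatment period, and Protocol 8 asks: "Does sustained rituximab therapy have long-term benefit beyond the treatment period". For this the plan also offers three other outputs:
- Kaplan-Meier relapse-free rates at 24 and 48 months from enrolment, by arm with confidence intervals (SAP 10.1).
- The proportion of patients maintaining remission at the same two times (secondary endpoint 1). The SAP gives no between-arm method for it.
- Time to a major or second minor relapse, and time to a major relapse (SAP 10.2). Both mirror the primary analysis and are called exploratory.

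**The concern.** Once a patient has had a first relapse, that patient leaves the risk set. If rituximab works during treatment, more control patients leave before the cut. If those who leave tend to be the more relapse-prone, the remaining controls are a lower-risk group than the remaining rituximab patients. The late hazard ratio then mixes any lasting treatment effect with this difference in composition. Neither document mentions the conditioning, limits the interpretation of the late result or plans a sensitivity analysis.

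At stake is the reading of a test that sits inside the closed procedure and is labelled post-treatment. A null or reversed value could be taken as loss or reversal of benefit when it partly reflects who was left to relapse.

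**Working it through.** **Inputs from the documents.** 160 patients randomised 1:1; "relapse-free rate of 75% and 50% at 4 years in the experimental and control arms respectively"; drop-out up to 5% at 2 years; 36 to 48 months from enrolment, so about 32 to 44 months after randomisation at month 4.

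**Input not in the documents.** Between-patient variation in relapse risk beyond the stratifiers, taken as a gamma frailty with mean 1 and variance θ = 0, 0.5, 1 or 2.

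**The plan's own figure.** The plan states: "A power of 90% is achieved under the alternative hypothesis of a hazard ratio of 0.42 at the 5% significance level with 58 observed relapses". Schoenfeld: 4 × (1.960 + 1.282)² / (ln 0.42)² = 56 events, and 58 events give power 0.91. The figure reproduces. No event number or power is stated for the late sub-hypothesis.

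**Who is left at the cut.** With constant hazards, relapse-free probability at 20 months is 0.50^(20/48) = 0.749 on control and 0.75^(20/48) = 0.887 on rituximab. So 25% and 11% have left through relapse. After drop-out, about 57 and 68 of 80 remain at risk. About 20 late relapses are then expected (about 15 with the 24-month cut). At a hazard ratio of 0.42 with no selection, the ungated late test has about 48% power (38% with the 24-month cut).

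**Size of the shift.** Under gamma frailty, mean frailty among the relapse-free is S^θ. The hazard ratio at the cut is therefore the true late ratio × (0.887/0.749)^θ = true ratio × 1.184^θ. The observed ratio is an average over the late window, so it was simulated: 80 per arm, 20-month cut, unadjusted Cox model, late test gated on the overall test. Ranges cover reasonable variations in the set-up.

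| θ | No late effect: at cut | No late effect: late window | True 0.42: at cut | True 0.42: late window | True 0.42: significant gated result |
|---|---|---|---|---|---|
| 0 | 1.00 | 0.99 | 0.42 | 0.42 | 43–49% |
| 0.5 | 1.09 | 1.07–1.09 | 0.46 | 0.46–0.48 | 34–40% |
| 1 | 1.18 | 1.16–1.18 | 0.50 | 0.52–0.55 | 24–32% |
| 2 | 1.40 | 1.29–1.34 | 0.59 | 0.63–0.67 | 13–19% |

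With the 24-month cut, the no-effect values at the cut are 1.11, 1.23 and 1.50 for θ = 0.5, 1 and 2. Moving the cut does not remove the problem.

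**False disadvantage.** With no late effect at the plan's rates, the late test taken alone is significant against rituximab in 3.7%, 5.4% and 9.0% of trials for θ = 0.5, 1 and 2. After gating this is about 0.2% or less, because the overall test seldom rejects in those trials.

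**Pilot-size separation.** If 24% and 71% had relapsed by 24 months, as in the pilot (Protocol 7.3, Figure 1), no late effect would appear as about 1.4 (θ = 0.5) or 1.7 to 1.9 (θ = 1). In one set-up, a gated result against rituximab then occurred in 13% and 33% of trials.

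**The randomised contrast.** Month 24 from enrolment is 20 months after randomisation: expected difference 0.887 − 0.749 = 0.138. Month 48 is 44 months after randomisation: 0.768 − 0.530 = 0.238, with a Greenwood SE of about 0.080.

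**The case against.** The late test is valid for what it literally tests, equal hazards among patients still at risk. Under the assumed frailty, a significant late result favouring rituximab would be conservative. Both points stand.

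A reader might infer that the late hazard ratio is necessarily biased against rituximab. The documents do not support that. With θ = 0 there is no bias, and the direction also assumes a similar on-treatment effect across patients. The pilot's move from 0.210 (early) to 0.323 (late) would fit such selection, but it rests on seven late relapses with an interval of 0.061 to 1.729 and shows nothing either way.

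A reader might also infer that the procedure is likely to declare a false post-treatment disadvantage. At the plan's own rates it is not. That risk needs pilot-size separation as well as frailty, and the pilot comparator was rituximab repeated only on relapse, not azathioprine.

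Nor is this the only planned look at durability. Secondary endpoint 1 addresses it directly, and SAP 10.2 adds late comparisons in which a first minor relapse does not end time at risk. But the first has no specified between-arm method, and the second is exploratory and still conditions on being event-free at the cut.

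Imprecision is also larger than the shift at moderate θ. With about 20 late relapses the SE of the log hazard ratio is about 2/√20 = 0.45, so the 95% interval spans a factor of about 2.4 each way, against a shift of 1.09 to 1.18 for θ of 0.5 to 1. This is a reason not to over-read the late ratio; it does not cure the conditioning.

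**Conclusion.** The point holds as one of interpretation and of a missing contrast. The conditioning follows from the endpoint and the model, whichever cut is used. Its numerical effect depends on a heterogeneity assumption that the documents neither give nor exclude. At the plan's rates the effect is modest attenuation and lost power: a true late ratio of 0.42 is seen as roughly 0.47 to 0.67, and the chance of detecting it falls from about 45% to about 36%, 25% and 14% for θ = 0.5, 1 and 2. Reversal is a material risk only with much larger on-treatment separation. The overall primary test, which includes everyone randomised, is unaffected.

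A reader might conclude that a month-48 difference should replace the late ratio as the sole basis for statements on durability. That goes too far: the difference carries forward benefit gained on treatment, so the two quantities answer different questions and belong together.

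**What to change.** - In SAP 10.1, add the between-arm difference in Kaplan-Meier relapse-free probability at months 24 and 48 from enrolment, with 95% CIs, in all randomised patients. Report it alongside the late hazard ratio for secondary objective 1.
- State that this difference includes benefit gained on treatment, so it shows whether benefit is retained, not whether new benefit accrues.
- Keep the late hazard ratio, label it as conditional on being relapse-free at the cut, and state that a null or reversed value will not by itself be read as absence or reversal of post-treatment benefit.
- Reconcile the 24-month cut (Protocol 16.1, SAP 8.9) with the 20-month cut (SAP 10.1). Twenty-four months after randomisation is month 28 from enrolment, past the end of the month 4–24 maintenance phase.

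Cost: SAP wording and a few lines of code, with no new data, since both time points are already estimated by arm. The downside is precision. An SE of about 8 points gives a 95% interval of about ±16 points at month 48. With 24 months of recruitment and closure 36 months after the last enrolment, only patients enrolled in the first 12 months can reach month 48. With even accrual that is half of the 160, and at the plan's rates about 80 × (0.530 + 0.768)/2 = 52 would still be relapse-free then, before drop-out.

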### 16.2 Interim Analyses

No interim analyses are planned, but an independent Data Monitoring Committee (Data and Safety Monitoring Board) will be convened to review efficacy and safety data, and will advise on the need for any additional analyses or alterations to the conduct or even continuation of the trial if there are major safety concerns.

### 16.3 Number of Subjects to be Enrolled

Enrolment will be ongoing until at least 160 patients are randomised. It is anticipated 190 patients will be required to be recruited to meet the goal of 160 patients randomized. Any patients in the induction phase when enrolment is halted will continue to follow the protocol and be randomised if the relevant criteria are met.

A power of 90% is achieved under the alternative hypothesis of a hazard ratio of 0.42 at the 5% significance level with 58 observed relapses. Randomising 160 patients will achieve this over the course of the study assuming a drop-out rate up to 5% at 2 years and a relapse-free rate of 75% and 50% at 4 years in the experimental and control arms respectively.

Based on data from the Cambridge cohort study, the overall hazard ratio is estimated (95% confidence interval) as 0.230 (0.116, 0.458) based on 37 observed relapses. For the early period the hazard ratio estimate is 0.210 (0.098, 0.449) based on 30 observed relapses. For the late period the hazard ratio estimate is 0.323 (0.061, 1.729)

based on seven observed relapses. Hence the sample size/power calculations are robust as they are based on a hazard ratio of 0.42 under the alternative hypothesis; the value of 0.42 is at the upper end of the confidence intervals for the overall and early period hazard ratios from the pilot data. The projected drop-out rate is based on the recently published EUVAS IMPROVE trial (16). It justifies the assumption of a rate below 5% in the second year.

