## 9 Trial Design

### 9.1 Statement of Design

RITAZAREM is a multi-centre, international, open label, randomised controlled trial in relapsing AAV. Patients will be randomised, 1:1, to receive fixed interval repeat rituximab dosing or azathioprine maintenance therapy.

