### **12.4 Long-Term Follow-up Assessments**

All patients will be followed until the last patient to be recruited has completed 36 months from study entry. With a two year recruitment period the median duration of follow-up will be 48 months from entry (range 36-48 months).

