## 7 Sample Size

(ICH E3; 9.7.2. ICH E9; 3.5)

Enrolment will be ongoing until 160 patients are randomised. It is anticipated 190 patients will be required to be recruited to meet the goal of 160 patients randomized. Any patients in the induction phase when enrolment is halted will continue to follow the protocol and be randomised if the relevant criteria are met.

A power of 90% is achieved under the alternative hypothesis of a hazard ratio of 0.42 at the 5% significance level with 58 observed relapses. Randomising 160 patients will achieve this over the course of the study assuming a drop-out rate up to 5% at 2 years and a relapse-free rate of 75% and 50% at 4 years in the experimental and control arms respectively.

Based on data from the Cambridge cohort study, the overall hazard ratio is estimated (95% confidence interval) as 0.230 (0.116, 0.458) based on 37 observed relapses. For the early period the hazard ratio estimate is 0.210 (0.098, 0.449) based on 30 observed relapses. For the late period the hazard ratio estimate is 0.323 (0.061, 1.729) based on seven observed relapses. Hence the sample size/power calculations are robust as they are based on a hazard ratio of 0.42 under the alternative hypothesis; the value of 0.42 is at the upper end of the confidence intervals for the overall and early period hazard ratios from the pilot data. The projected drop-out rate is based on the recently published EUVAS IMPROVE trial (16). It justifies the assumption of a rate below 5% in the second year.

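### The plan says 160 randomised patients will yield 58 relapses, but its own follow-up yields about 51 to 57; the power loss is small, 0 to 3 points

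*Protocol*

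**What the plan says.** SAP 7, in the same words as protocol 16.3, sets the target: "A power of 90% is achieved under the alternative hypothesis of a hazard ratio of 0.42 at the 5% significance level with 58 observed relapses". SAP 10.1 makes the test two-sided. Protocol 16.3 continues: "Randomising 160 patients will achieve this over the course of the study assuming a drop-out rate up to 5% at 2 years", with "a relapse-free rate of 75% and 50% at 4 years in the experimental and control arms respectively". It later supports the drop-out figure from an earlier maintenance trial: "It justifies the assumption of a rate below 5% in the second year". Allocation is equal (protocol 9.1): "Patients will be randomised, 1:1, to receive fixed interval repeat rituximab dosing or azathioprine maintenance therapy".

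Follow-up is set elsewhere:

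- Protocol 16.1 gives a 24-month recruitment period and a 48-month maximum, and says: "The minimum follow-up period will be 24 months of treatment plus 12 months post-treatment, totalling 36 months".
- Protocol 12.4 counts from entry: "the median duration of follow-up will be 48 months from entry (range 36-48 months").
- Protocol 16.4 and SAP 8.1 close the trial 36 months after the last enrolment. Neither waits for a number of relapses.
- The primary endpoint runs from randomisation (protocol 9.6.1). SAP 5.2.1 takes the month 4 visit as time zero, and a footnote in SAP 10.1 equates 48 months from enrolment with 44 months after randomisation.

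**The concern.** The relapse-free rates are stated at 4 years, but the endpoint clock starts four months into a study that lasts at most 48 months, and late recruits are followed for only 36. Nobody can be observed for 48 months after randomisation. The SAP applies the four-month offset to its Kaplan-Meier time points but not to its sample size.

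Both documents may therefore attribute to 160 patients a relapse count that the planned follow-up does not supply. A borderline or null result would then be read against a slightly overstated design.

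**Working it through.** **Inputs.** 160 randomised, 80 per arm; 75% and 50% relapse-free at 4 years; drop-out 5% at 24 months; hazard ratio 0.42; two-sided 5%; 24-month recruitment; close 36 months after the last enrolment; 48-month cap; time zero at month 4. All are from the sections cited above. Assumed here, because the documents do not state them: uniform accrual, exponential drop-out, and the shape of the relapse hazard.

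**1. The plan's event target and power.** Schoenfeld: d = 4(1.96 + 1.2816)² / (ln 0.42)² = 55.8, so 56 relapses. With 58, power = Φ(√58/2 × |ln 0.42| − 1.96) = 91.0%. The pairing of 58 relapses with 90% is sound and carries a margin of 2.

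**2. Relapses if everyone has the full 4 years.** Without drop-out: 80 × 0.25 + 80 × 0.50 = 60. With drop-out hazard δ = −ln(0.95)/24 = 0.00214 per month and a constant relapse hazard λ, the chance of an observed relapse within a months is λ/(λ+δ) × [1 − exp(−(λ+δ)a)]. With λ = −ln(0.75)/48 = 0.00599 and ln 2/48 = 0.01444, and a = 48, the total is 57.3. If the 4 years run from enrolment (44 months after randomisation) and all are followed to that point, it is 57.5. So a figure near 58 needs patients to average the whole 4-year period.

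**3. Planned time at risk.** For entry at month e, uniform on 0 to 24, time at risk is min(48, 60 − e) − 4. Half the patients have 44 months and half are spread over 32 to 44; the mean is 0.5 × 44 + 0.5 × 38 = 41 months. Uniform accrual also reproduces the protocol's median of 48 months from entry.

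**4. Constant hazard, planned follow-up, 5% drop-out.** For the control arm with the 4 years from randomisation, λ+δ = 0.01658 and λ/(λ+δ) = 0.871. The exponential term is 0.482 at 44 months and averages 0.534 over 32 to 44, so 0.508 overall. Relapses: 80 × 0.871 × (1 − 0.508) = 34.3. The rituximab arm gives 16.7 in the same way, 51.0 in all.

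**5. Front-loaded hazard.** The same calculation with a Weibull curve, S(t) = S₄^((t/T)^k), where S₄ is the 4-year rate, T is 48 or 44 months, and k is 0.7 or 0.5.

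| Hazard | 4 years from randomisation | 4 years from enrolment |
|---|---|---|
| Constant | 51.0 relapses, 87.2% | 54.6, 89.3% |
| Weibull, k = 0.7 | 53.3, 88.6% | 55.9, 90.0% |
| Weibull, k = 0.5 | 55.0, 89.6% | 56.9, 90.5% |

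Powers use the formula in step 1. A log-rank simulation of the first cell (20,000 trials) gave 86.5%, close to the formula. If the 36 to 48 months were counted from randomisation instead, against protocol 12.4, a constant hazard would give 54.6 relapses and 89.4%.

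**The case against.** **The hazard need not be constant.** This stands. The protocol's pilot cohort points to early relapse: 30 of its 37 relapses fell in the early period. Front-loading narrows the gap and brings power to 88.6 to 90.5%. The relapse count still stays below 58 when drop-out is 5%.

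**5% is an upper bound.** Also true. With no drop-out and a constant hazard, the counts are 53.1 (88.5%) and 56.8 (90.5%). Only a strongly front-loaded hazard (k = 0.5), no drop-out and a 4-year clock from enrolment together reach 58 (58.3). That is a favourable corner, not the stated assumption.

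**The rates imply a slightly stronger effect.** ln 0.75/ln 0.50 = 0.415. With that value, 51.0 and 54.6 relapses give 88.1% and 90.1% power. The counts do not change.

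**160 is a floor.** Protocol 16.3 says at least 160, and patients in induction at the halt are also randomised if eligible. At 190/24 = 7.9 enrolments a month, about 32 would be in induction; at 160/190 about 27 would follow, 187 in all, and 51.0 × 187/160 = 59.6 relapses. With 175 randomised the figure is 55.8 (90.0%). This could close the gap. But 187 implies about 190 + 32 = 222 enrolments, against the 190 anticipated, and the sample size sections attribute the 58 relapses to 160.

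**Materiality.** The hazard ratio of 0.42 was chosen well above the pilot estimate of 0.230, an uncertainty that dwarfs three points of power. This bears on the size of the point, not on whether the sentence is right.

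**Conclusion.** The relapse count attributed to 160 patients does not follow from the planned follow-up. With uniform accrual, exactly 160 randomised and 5% drop-out at 2 years, expect about 51 to 55 relapses under a constant hazard and 53 to 57 under a front-loaded one: 1 to 7 fewer than 58. Power is about 87 to 90.5%, a loss of 0 to 3 points. The point is modest, and it concerns the accuracy of a stated design figure.

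Stronger readings that the documents do not support:

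- A reader might infer that the trial is materially underpowered or needs more patients. It does not: 56 relapses suffice by Schoenfeld, and several plausible scenarios reach 90%.
- A reader might apply Freedman's formula, which asks for 63 relapses, and find a larger loss. That formula does not match the plan's 58, and the simulation agrees with Schoenfeld.
- A reader might take 60 relapses less drop-out as the origin of 58. The documents give no derivation, and that route gives 57.3 to 57.5.
- A reader might see a contradiction between 5% at 2 years and below 5% in the second year, and infer about 10% by 2 years. The second phrase is ambiguous; neither document states 10%.

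**What to change.** In protocol 16.3 and SAP 7, replace the claim that 160 patients will deliver the 58 relapses with the expected relapses and power for 32 to 44 months after randomisation. State alongside it:

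1. the assumed hazard shape and accrual pattern;
2. whether the 4 years run from randomisation or from enrolment;
3. one drop-out figure, used in both sentences;
4. that 160 is a minimum, and that patients in induction when enrolment halts may add relapses.

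Under a constant hazard the entry would read about 51 to 55 relapses and 87 to 89% power; the sponsor may justify a front-loaded hazard and report about 53 to 57 and 89 to 90.5%. The cost is one reworded paragraph in each document and a stated power that may be slightly less favourable. No patients, visits or analyses are added.
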